Exploratory Objectives

1) Track occurrence of infections, deep venous thrombosis, vascular events and falls in the study population.
2) To evaluate relationship between CYP24, 27B1, SNPs and serum 25(OH) vitamin D response to oral D3 supplementation.

Study Design: Double-blinded, parallel, placebo controlled randomized 2-group complete cross-over design with 12 week washout period. 103 patients are expected to enroll over 11 year period.

[figure not shown]
Treatment Plan: Eligible men will be randomly assigned to two groups in 1:1 ratio.

Group A will receive 6,000 IU daily of vitamin D3 provided as 3 capsules of 2000 IU each.

Group B will receive a placebo provided as 3 capsules of a rice based placebo.

Treatment Duration: Participants will be followed for 36 weeks and then crossed over after a wash out period of 12 weeks and followed for another 36 weeks.

Number of Participants: Each group will be comprised of approximately 50 men. Those who are not able to complete the study will be replaced.

Dose Modification:

- 1). If a participant's 25(OH) D3 level reaches > 200ng/ml with 6000 IU or 3 capsules a day, or any \geq grade 3 toxicity possibly related to cholecalciferol develops, 25(OH) D3 or placebo will be discontinued for 4 weeks. Treatment will then be resumed at lower dose of 4000 IU or 2 capsules a day. If a participant misses some period of time off the study drug, the treatment would be resumed such that the participant completes a total of 36 weeks on the study drug.
- 2). If a participant's 25(OH) D3 level reaches > 200ng/ml with the lower dose modification of 4000 IU or 2 capsules a day, or any grade 3 toxicity develops, 25(OH) D3 or placebo will be discontinued for 4 weeks. Treatment will then be resumed at lower dose of 2000 IU or 1 capsule a day.
- 3). If a participant's 25(OH) D3 level reaches > 200ng/ml with the lower dose modification of 2000 IU or 1 capsule a day, or any grade 3 toxicity develops, the participant will then be taken off study.
- 4). Participants that drop out after the first treatment period (36 weeks) will be included in the analysis but will require enrolling additional participants such that we have evaluable data on 100 participant-periods. An intention to treat analysis will be done.

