- 4) Serum alkaline phosphatase, aspartate aminotransferase (AST/SGOT), alanine aminotransferase (ALT/SGPT), total serum bilirubin, BUN, serum creatinine, electrolytes, calcium, phosphorous, total protein, albumin, glucose and LDH; Tumor biomarkers: PSA
- 5) Imaging studies for potential evaluable disease sites as clinically indicated and at clinician's discretion.
- 6) Baseline toxicity evaluation to document residual toxicity and baseline symptoms
- 7) 25(OH) D3 level
- 8) 24 hour urinary calcium and creatinine
- 9) Research labs (PTH, serum/DNA/Plasma samples)
- 10) All pretreatment PSA values done up to 2 years prior to enrollment will be recorded

Toxicity assessment will be done after 4 weeks of enrollment via a telephone assessment, thereafter will be done every 12 weeks at a clinic visit. Relevant laboratory data will be repeated every 12 weeks (please see the table 6.1). Investigational biomarkers will also be done with these laboratory tests every 12 weeks.

Patients will be continued on a treatment group for 36 weeks and then will have a 12 week washout period where they will be off any study drug or placebo. After this 12 week washout period, patients will be crossed-over with follow up every 12 weeks for another 36 weeks (total = 84 weeks) with assessments similar to those done at 36 week visit.

Study Duration: 11 years

Study Medication

Oral Vitamin D3 supplementation will be provided as capsules of 2000 IU each (manufacturer-Vital Nutrients). Patients will be advised to take 3 capsules once a day to provide 6,000 IU of Vitamin D3.

Cholecalciferol is to be taken orally as a single AM dose.

An identical placebo containing rice powder will be provided by the manufacturer.

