6.0 Study design

Study design

Double-blinded, parallel, placebo controlled randomized 2-group complete cross-over design with 12 week washout period.

Participant Assignment

Eligible patients will be randomly assigned to two groups in 1:1 ratio.

Group A will receive 6,000 IU daily of vitamin D3 (3 capsules of 2000 IU pills).

Group B will receive an identical placebo.

[figure not shown]
Each group will be comprised of approximately 50 patients. Patients who are not able to complete the study will be replaced.

Cross-over will be done after a period of 36 weeks followed by 12 weeks washout period. After 12 week washout period, patients on either arm will be crossed over to receive the drug on the other arm (patients who were on vitamin D arm will get crossed-over to receive placebo, while patients on placebo arm will be crossed-over to receive vitamin D).

They will be stratified randomization based on the Gleason score (less than or equal to 6, OR greater than 6) as well as the season of entry (winter/spring versus summer/fall). Seasonal stratification assignment will be based on the date of randomization:

If randomized between 12/22 and 6/21, it will be considered the winter/spring group and if randomized between 6/22 and 12/21 it will be the summer/fall group.

After completion of study, patient may choose to continue vitamin D if they desire.

Duration of the trial

Patients will be followed for 36 weeks after randomization followed by a washout period of 12 weeks and then be crossed over and followed for an additional 36 weeks (total 84 weeks). 103 patients are expected to enroll over an 11 year period.

Dose Modification:

- 1). If a patient's 25(OH) D3 level reaches > 200ng/ml with 6000 IU or 3 capsules a day, or any \geq grade 3 toxicity possibly related to cholecalciferol develops, 25(OH) D3 or placebo will be discontinued for 4 weeks. Treatment will then be resumed at lower dose of 4000 IU or 2 capsules a day. If a patient misses some period of time off the study drug, the treatment will be resumed such that the patient completes a total of 36 weeks on the study drug.
- 2). If a patient's 25(OH) D3 level reaches > 200ng/ml with the lower dose modification of 4000 IU or 2 capsules a day, or any grade 3 toxicity develops, 25(OH) D3 or placebo will be discontinued for 4 weeks. Treatment will then be resumed at lower dose of 2000 IU or 1 capsule a day.

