- 3). If a patient's 25(OH) D3 level reaches > 200ng/ml with the lower dose modification of 2000 IU or 1 capsule a day, or any grade 3 toxicity develops, the patient will then be taken off study.
- 4). Patients that drop out after the first treatment period (36 weeks) will be included in the analysis but will require enrolling additional patients such that we have evaluable data on 100 patient-periods. An intention to treat analysis will be done.
- 5). If patient misses a daily dose of vitamin D3, or placebo, he should skip it and continue to take it as scheduled the following day. The patient should write down the day of the missed dose in the diary and should bring the diary with him on the day of physical. If patient misses more than 1/3 rd of the doses in a 12 week period, the patient will be taken out of the study and will be replaced by another patient.
- 6). At the end of study, patients may choose to continue taking vitamin D3 replacement per personal preferences.

6.1 Study Schedule: Pre-treatment evaluations are described in section 5.0 and are repeated here for sake of convenience.

Parameters	Pre-study ^e	4 weeks (+/- 7 days)	12 weeks (+/- 7 days)	24 weeks (+/- 7 days)	36 weeks (+/- 7 days)	4 weeks f/u ^a (+/- 7 days)
Physical Exam, Medical History, Vital Signs and ECOG(Wt, temperature, BP, pulse and respiration rate)	X			X		
Height	X					
Toxicity assessment	X	X^a	X	X	X	X^a
Serum alkaline phosphatase, aspartate aminotransferase (AST/SGOT), alanine aminotransferase (ALT/SGPT), total serum bilirubin, BUN, serum creatinine, electrolytes, calcium, phosphorous, total protein, albumin, glucose and LDH	X		X	X	X	
Serum 25(OH)D3	X		X	X	X	
PTH^b	X		X	X	X	
PSA	X		X	X	X	
24 hr urinary calcium and creatinine	X		X^g	X^g	X	
Assessment of infection, fall, fracture, thrombosis	X		X	X	X	
Investigational Biomarker samples^{b, c} and DBBR Blood Draw	X	X	X	X	X	
Radiographic study(Computed tomography and/ or bone scan)^f	X		X	X	X	
Study drug compliance assessment		X	X	X	X	
Nurse visit: ECOG, Wt, temperature & BP			X		X	

a- Telephone assessment

b- Performed in the lab. See Sec. 6.1 "Monitoring"

c- DNA, serum, plasma isolated through ongoing Vitamin D assessment protocol (only for patients at Roswell Park).

d- After a wash-out period of 12 weeks, patients will be crossed over. Patients would be followed every 12 weeks with similar plan.

e- Pre study evaluations are to be done within 4 weeks of registration. Complete history to be done at pre study evaluation.

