7.0 Criteria for Discontinuation

- 1) Patient does not comply with study guidelines.
- 2) Patient wants to withdraw
- 3) Unacceptable side effects attributed to study treatments. e.g. development of genitourinary stones or grade 2 or higher hypercalcemia
- 4) Patient unable to tolerate the drug. e.g. persistent nausea and vomiting for more than 48hrs or any grade 3 or higher toxicity attributed to study drug.
- 5) Creatinine \geq 2.5 X baseline.
- 6) Need for any active treatment for prostate cancer on clinician's discretion.

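### The dose-reduction ladder changes its toxicity trigger below the top dose, losing both the relatedness condition and the grade 4 coverage, and section 7.0 conflicts with it instead of repairing it

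*Combined protocol and SAP*

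**What the plan says.** The ladder appears twice, under Dose Modification in the Study Summary and again in section 6.0. The toxicity triggers have the same content in both.

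- **Item 1 (6000 IU, 3 capsules).** The trigger is "grade 3 toxicity possibly related to cholecalciferol develops", preceded by a greater-than-or-equal sign. The consequence is a 4-week hold, then resumption at 2 capsules.
- **Item 2 (4000 IU, 2 capsules).** "or any grade 3 toxicity develops, 25(OH) D3 or placebo will be discontinued for 4 weeks", then resumption at 1 capsule.
- **Item 3 (2000 IU, 1 capsule).** "or any grade 3 toxicity develops, the patient will then be taken off study". The Study Summary has "or any grade 3 toxicity develops, the participant will then be taken off study".

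Each item also has a separate trigger, a 25(OH)D3 level above 200 ng/ml, which is the same at all three steps and is not in question.

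Section 7.0 (Criteria for Discontinuation) gives, as an example under item 4, "any grade 3 or higher toxicity attributed to study drug". Its item 3 gives genitourinary stones and hypercalcemia of grade 2 or above as examples of unacceptable side effects attributed to treatment.

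On men who leave, section 6.0 says: "Patients who are not able to complete the study will be replaced". Item 4 of the same list states an intention-to-treat analysis.

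**The concern.** A single ladder would be expected to use one definition of the event that moves a man down it. Here the definition changes after the first step in two ways: attribution is no longer required, and the grade range is no longer open at the top. The same unrelated grade 3 event would leave a man at 3 capsules where he is, halve the dose of a man at 2 capsules (4000 to 2000 IU, one third of the assigned 6000 IU), and end participation for a man at 1 capsule.

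At stake are the vitamin D exposure under test and the PSA follow-up of men who are removed and then replaced, in a trial that also promises intention to treat. Uniform conduct is at stake too. Two investigators could reasonably apply items 2 and 3 differently, one literally and one by carrying item 1's conditions forward.

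**Working it through.** The plan gives no figure on this point, so the check is a comparison of the texts.

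**Step 1: does the word toxicity already imply a drug cause?** It does not. Item 1 adds a relatedness condition to the word, which would be redundant if relatedness were implied. The Study Summary's pretreatment list includes "Baseline toxicity evaluation to document residual toxicity and baseline symptoms", so the word is used before any study drug is given; sections 5.0 and 6.1 also call for a baseline toxicity evaluation. Section 10.2.1 provides a separate five-level relatedness scale, so grade and attribution are two distinct judgments in this protocol.

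**Step 2: what each rule does, read literally.**

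| Event | Item 1, 3 capsules | Item 2, 2 capsules | Item 3, 1 capsule | Section 7.0 item 4, any dose |
|---|---|---|---|---|
| Grade 3, possible or stronger | hold, reduce | hold, reduce | off study | discontinuation, if attributed |
| Grade 3, unlikely or unrelated | no action | hold, reduce | off study | not covered |
| Grade 4, possible or stronger | hold, reduce | not named | not named | discontinuation, if attributed |
| Grade 4, unlikely or unrelated | no action | not named | not named | not covered |

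**Step 3: what the table shows.**

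- Row 2: the consequence depends on whether the man has already been reduced, with no reason given.
- Rows 2 and 4 at the lower steps: an unrelated grade 3 event triggers action while an unrelated grade 4 event does not. That ordering is hard to read as intended.
- Rows 1 and 3: section 7.0 item 4 reaches attributed events at every dose, but it discontinues where item 1, and for grade 3 item 2, hold and resume lower. Section 7.0 item 3 overlaps as well, since attributed grade 3 hypercalcemia meets both it and item 1.
- Section 7.0 does not say which level of the section 10.2.1 scale counts as attributed, so the overlap with item 1's lower threshold (possible) is itself unclear.

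**Step 4: how many men?** The documents give no rate of grade 3 or 4 events and no expected number of dose reductions, so no count can be derived. One route onto the lower steps looks narrow on the protocol's own figures. The level trigger of 200 ng/ml is 200 × 2.5 = 500 nmol/L by the conversion in section 1.4, and that section describes levels of about 75 to 220 nmol/L across intakes of 800 to 20,000 IU a day. Most reductions would therefore have to come from toxicity. Of the 84 weeks per man, 84 − 12 = 72 are on study capsules, and only the time after a reduction counts.

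**The case against.** The strongest reply is that items 2 and 3 are shorthand for item 1, that few men will reach them, and that section 7.0 covers the serious cases.

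- **Shorthand.** This is possible, but the text does not say so, and the same omission stands in both places.
- **Few men.** This stands. If section 7.0 item 4 governs, a man with an attributed grade 3 event may be discontinued before he reaches the lower steps at all. That makes the affected group smaller, but only by exposing the second conflict.
- **Narrow difference.** For grade 3 events, item 1 and items 2 and 3 differ only for events rated unlikely or unrelated, because possible already includes events that other factors could have caused. This also stands.
- **Data loss partly handled.** Men who drop out after the first treatment period stay in the analysis, a mixed model is planned, and under blinding the rule reads the same for both arms. The documents give no basis for claiming a biased treatment effect, and none is claimed here.

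Three stronger readings are tempting and do not hold:

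- A reader might infer that tolerability is counted differently by dose level. It is not. Both reporting tables in section 10.3 require every grade 3 and 4 event whatever its attribution, and section 11 compares toxicity as a difference in proportions, with no analysis by dose level.
- A reader might infer that grade 4 events at the lower doses go wholly unaddressed. Attributed ones fall under section 7.0 item 4, and unrelated ones trigger nothing under item 1 either.
- A reader might infer that the protocol expects many unrelated events because it follows infections, thrombosis, vascular events and falls. Section 2.2 lists these only as exploratory tracking and states no rates.

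**Conclusion.** The inconsistency is real and sits in an operative rule for dosing and removal. The ladder uses two toxicity triggers, and section 7.0 attaches a different consequence to events the ladder also governs. The practical size is probably small: only men already reduced are exposed to the unrelated-event problem. The conflict with section 7.0 is wider, since it arises for an attributed event of grade 3 or above at the starting dose.

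The conclusion rests on reading items 2 and 3 as written. If the sponsor meant item 1's conditions to carry down, the trigger problem is one of wording only, but the conflict with section 7.0 remains.

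**What to change.** Reconcile Dose Modification items 1 to 3, in the Study Summary and section 6.0, with each other and with section 7.0 items 3 and 4. For every dose level, state once and consistently the grade range, the attribution requirement in terms of the section 10.2.1 scale, and the consequence. Where the ladder and section 7.0 both apply, say which takes precedence. Which trigger and which consequence should apply is for the sponsor's clinicians to decide; no rule is proposed here.

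The cost is a wording amendment to the Study Summary, section 6.0 and section 7.0. No new assessment is needed, because grade and relatedness are already recorded for adverse events under section 10.2.1.

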7.0 Criteria for Discontinuation

- 1) Patient does not comply with study guidelines.
- 2) Patient wants to withdraw
- 3) Unacceptable side effects attributed to study treatments. e.g. development of genitourinary stones or grade 2 or higher hypercalcemia
- 4) Patient unable to tolerate the drug. e.g. persistent nausea and vomiting for more than 48hrs or any grade 3 or higher toxicity attributed to study drug.
- 5) Creatinine \geq 2.5 X baseline.
- 6) Need for any active treatment for prostate cancer on clinician's discretion.

7.1 Criteria for initiation of more aggressive treatment

- 1) PSADT < 3 year.
- 2) Tumor grade progression (e.g. Gleason = or > 7).
- 3) Clinical progression.
- 4) Patient choice.
- 5) Physician discretion.

8.0 Drug information

8.1 Vitamin D3 (Cholecalciferol)

Availability

Vitamin D3 is the standard replacement approach and would be utilized for the purpose of our study. Oral Vitamin D3 supplementation will be provided as capsules provided by Vital Nutrients. Patients will be advised to take 3 capsules once a day to provide 6,000 IU of Vitamin D3.

Administration

Cholecalciferol is to be taken orally as a single AM dose.

Side Effects of Cholecalciferol

Reported side effects are all related to hypercalcemia which can result in nausea, vomiting, constipation, polyuria, nocturia, polydipsia, hypercalcemia and genitourinary stones and rarely cardiac arrhythmias. Refer to product monograph for more details.

8.2 Placebo

Oral placebo will be available in rice powder based capsules which appear identical to vitamin D capsules. It will again be dispensed as 3 capsules a day as a single AM dose.

8.3 Drug Availability

Cholecalciferol (D3) and identical placebo are available as capsules provided by Vital Nutrients.

8.4 Drug ordering:

Cholecalciferol (D3) is commercially available but will be provided free of charge to patient enrolled in this clinical trial. It will be ordered by the Investigational Drug Service through the appropriate grant.

8.5 Agent Inventory records:

The IDS will maintain inventory and dispensing records on the NIH2564 DARF.

8.6 Administration:

Cholecalciferol (D3) and placebo will be taken orally.

9.0 Ethical Requirements

The participant must give a written, informed consent to participate in study. Participants may withdraw from the study at any time, for any reason, without prejudice to their present or future care. In outlining the study, the principal investigator will explain the treatment plan; the potential hazards and benefits to the patient and proposed visit schedule to evaluate the effects of the study. Informed consent will be signed by the participant and an investigator.

10.0 SAFETY EVALUATION

10.1 Adverse Events

An adverse event or adverse experience (AE) is any untoward medical occurrence associated with the use of a drug in humans, whether or not considered drug related. Therefore, an AE can be ANY unfavorable and unintended sign (including an abnormal laboratory finding), symptom, or disease temporally associated with the use of a medicinal (investigational) product, whether or not considered related to the medicinal (investigational) product (attribution of ‘unrelated’, ‘unlikely’, ‘possible’, ‘probable’, or ‘definite’).

An AE is considered “unexpected” if it is not listed in the investigator brochure or is not listed at the specificity or severity that has been observed; or if an investigator brochure is not required or available, is not consistent with the risk information described in the general investigational plan in other study-related documents.

10.1.1 Diagnosis Versus Signs and Symptoms

If known, a diagnosis should be recorded on the CRF rather than individual signs and symptoms (e.g., record only liver failure or hepatitis rather than jaundice, asterixis, and elevated transaminases). However, if a constellation of signs and/or symptoms cannot be clinically characterized as a single diagnosis or syndrome at the time of reporting, each individual event should be recorded as an AE or SAE on the CRF. If a diagnosis is subsequently established, it should be reported as follow-up information.

10.1.2 Adverse Events Occurring Secondary to Other Events

In general, AEs occurring secondary to other events (e.g., cascade events or clinical sequelae) should be identified by their primary cause. For example, if severe diarrhea is known to have resulted in dehydration, it is sufficient to record only diarrhea as an AE or SAE on the CRF. However, clinically significant AEs occurring secondary to an initiating event that are separated in time should be recorded as independent events on the CRF. For example, if a severe gastrointestinal hemorrhage leads to renal failure, both events should be recorded separately on the CRF.

10.1.3 Abnormal Laboratory Values

Only clinically significant laboratory abnormalities that require active management will be recorded as AEs or SAEs on the CRF (e.g., abnormalities that require study drug dose modification, discontinuation of study treatment, more frequent follow-up assessments, further diagnostic investigation, etc.).

If the clinically significant laboratory abnormality is a sign of a disease or syndrome (e.g., alkaline phosphatase and bilirubin 5 x the upper limit of normal associated with cholecystitis), only the diagnosis (e.g., cholecystitis) needs to be recorded on the Adverse Event CRF.

If the clinically significant laboratory abnormality is not a sign of a disease or syndrome, the abnormality itself should be recorded as an AE or SAE on the CRF. If the laboratory

abnormality can be characterized by a precise clinical term, the clinical term should be recorded as the AE or SAE. For example, an elevated serum potassium level of 7 mEq/L should be recorded as “hyperkalemia”.

Observations of the same clinically significant laboratory abnormality from visit to visit should not be repeatedly recorded as AEs or SAEs on the CRF, unless their severity, seriousness, or etiology changes.

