2.1 Secondary Objectives

- 1) To examine the pattern of response of PSA dynamics as well as the absolute change in PSA following vitamin D3 supplementation.
- 2) Assess the toxicity of vitamin D3 supplementation in men with prostate cancer.

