- Guidelines for Routine Adverse Event Reporting for Phase 1 Studies
(Regardless of Expectedness)**

Attribution	Grade 1	Grade 2	Grade 3	Grade 4
Unrelated	X	X	X	X
Unlikely	X	X	X	X
Possible	X	X	X	X
Probable	X	X	X	X
Definite	X	X	X	X

- Guidelines for Routine Adverse Event Reporting for Pilot, Phase 2, and Phase 3 Studies (Regardless of Expectedness)**

Attribution	Grade 1	Grade 2	Grade 3	Grade 4
Unrelated			X	X
Unlikely			X	X
Possible	X	X	X	X
Probable	X	X	X	X
Definite	X	X	X	X

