In addition to the data analysis described above which analyze $\text{Log}_2(\text{PSA})$, for the men who have 3 or more PSA values from the same laboratory over a period of 18 months or more prior to enrollment, PSA velocity (PSAV) will be calculated and compared to a PSA velocity obtained by analysis of the PSA's during the 2 periods of investigation on the study (the 36 weeks on placebo and the 36 weeks on treatment). Specifically, PSAV can be analyzed as a summary statistics as follows: PSAV will be calculated for the pre-study period, the first 36 week study period, and the second 36 week study period for each participant by simple linear regression. As a preliminary step, summary statistics such as sample mean and standard deviations will be calculated for each group at each period (pre study, first 36 weeks, and second 36 week). Furthermore, the difference in the PSAV caused by vitamin D3 treatment will be tested using two-sample t test comparing the means of differences (first 36 week - second 36 week) in PSAV for the first group (vitamin D3 treatment then control sequence) and the second group (control then vitamin D3 treatment sequence).

The toxicity will be compared as difference in proportion with 95% confidence intervals. Survival would be evaluated on an exploratory basis but no comparison would be made between groups. Relationship between CYP24, 27B1, SNPs and serum 25(OH)D3 vitamin D response to oral D3 supplementation will again be done as an exploratory analysis. We are developing assays to help in this regards and methods for these exploratory analysis would be added as these assays are formulated.

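### Section 11 does not say what counts as toxicity; if it means CRF adverse events, unactioned grade 1 calcium and creatinine rises go uncounted

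*Combined protocol and SAP*

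**What the plan says.** - Section 2.1 makes toxicity a secondary objective: "Assess the toxicity of vitamin D3 supplementation in men with prostate cancer". Its whole analysis is one sentence in section 11: "The toxicity will be compared as difference in proportion with 95% confidence intervals". That sentence does not name the events, grades, time window or data source, or say how a man's two treatment periods are handled.
- Section 8.1 identifies the main expected harm: "Reported side effects are all related to hypercalcemia".
- Section 10.1 defines an adverse event broadly, as "ANY unfavorable and unintended sign (including an abnormal laboratory finding), symptom, or disease temporally associated with the use of a medicinal (investigational) product". Section 10.1.3 is narrower about what reaches the CRF: "Only clinically significant laboratory abnormalities that require active management will be recorded as AEs or SAEs on the CRF". Its examples of active management are broad: "abnormalities that require study drug dose modification, discontinuation of study treatment, more frequent follow-up assessments, further diagnostic investigation, etc".
- Section 7.0 gives "development of genitourinary stones or grade 2 or higher hypercalcemia" as examples of unacceptable side effects attributed to treatment, which are grounds for discontinuation.
- Section 10.3 prints two routine reporting tables. The Phase 1 table covers every grade and attribution. The table for pilot, phase 2 and phase 3 studies leaves out grade 1 and 2 events judged unrelated or unlikely. The text does not say which one applies.
- Section 6.1 schedules the chemistry panel, including calcium, albumin and creatinine, before the study and at weeks 12, 24 and 36, with a similar plan after cross-over. Section 4.1 gives the formula for albumin-corrected calcium. Section 11 plans no comparison of these values.

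**The concern.** The main expected harm of the study drug is defined by a laboratory value, and that value is measured on a fixed schedule under both treatments. The only rules for recording harms, however, are those in section 10, and there a raised calcium becomes an adverse event through what the clinician does about it. If the toxicity proportion is built from those entries, the same calcium could count in one man and not in another, and a mild excess on vitamin D3 could be partly or wholly invisible. In a safety comparison, an error toward no difference is the unwelcome direction. The data that would avoid it are already being collected.

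**Working it through.** The plan gives no rate, margin, sample size or power for toxicity. Its only power statement concerns the PSA slope, so there is no figure to reproduce here. The check has two parts.

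**1. What happens to a raised calcium if the CRF adverse events are the source**

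| Finding | Recorded under section 10.1.3? |
|---|---|
| Grade 2 or higher, attributed to treatment | Yes: a discontinuation example in section 7.0, and discontinuation is active management |
| Grade 1, leading to extra follow-up or investigation | Yes: both are listed as active management. Section 6.1, note g, allows a 24-hour urine test after a calcium rise, at the clinician's discretion |
| Grade 1, no action taken | No |

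The loss is therefore confined to the last row, and the same reasoning applies to creatinine rises that prompt no action. Section 10.1.3 also says that the same abnormality should not be entered again at later visits unless its severity, seriousness or cause changes. In a cross-over, a finding that recurs in period 2 could then go unrecorded under the second treatment.

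**2. What the loss does to a difference in proportions**

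Let p1 and p0 be the true proportions on vitamin D3 and placebo, and f the share of cases recorded. With f taken as equal on both treatments:

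- recorded difference = f × (p1 − p0)
- recorded ratio = f·p1 / f·p0 = p1 / p0, unchanged
- 95% CI = difference ± 1.96 × √[a(1−a)/n + b(1−b)/n], with a = f·p1 and b = f·p0

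Assumptions, none from the documents: p1 = 10% and p0 = 2% for any-grade laboratory hypercalcemia, and the two treatment periods treated as independent. I take n = 100 per treatment, because section 6.0 plans about 50 men per group and each man is to receive both treatments.

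All cases counted: √(0.10×0.90/100 + 0.02×0.98/100) = √0.001096 = 0.0331, and 1.96 × 0.0331 = 0.065. Half recorded: √(0.05×0.95/100 + 0.01×0.99/100) = √0.000574 = 0.0240, and 1.96 × 0.0240 = 0.047.

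| Share recorded | D3 against placebo | Difference, points (95% CI) |
|---|---|---|
| All | 10% v 2% | 8.0 (1.5 to 14.5) |
| Half | 5% v 1% | 4.0 (−0.7 to 8.7) |
| A quarter | 2.5% v 0.5% | 2.0 (−1.4 to 5.4) |
| None | 0% v 0% | 0 |

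With every case counted, assumed rates of 5% v 1% give 4.0 (−0.7 to 8.7), and 15% v 3% give 12.0 (4.2 to 19.8). Section 6.0 also speaks of evaluable data on 100 patient-periods, which would be 50 per treatment. On that reading, 10% v 2% gives 8.0 (−1.2 to 17.2). The last row of the table is a bound, reached only if every case is an unactioned grade 1 rise.

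**The case against.** The strongest reply is that the plan never adopts the faulty definition. Section 11 does not say that toxicity is counted from adverse-event entries, and section 6.1 has a toxicity assessment row separate from the chemistry panel. A reader might infer that the endpoint is the filtered adverse-event count, but the documents leave the numerator open. That stands, and it is why the point is conditional. The silence is itself the first defect.

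A reader might also infer that mild hypercalcemia as a whole drops out. The breadth of active management and the discontinuation example rule that out; only grade 1 values with no response are lost.

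A third tempting reading is that attribution judgments create a spurious difference between the arms. The documents do not support it. The trial is double-blind with identical capsules, so a judgment that differs by arm would need knowledge of the assignment. Serum 25(OH)D3 is measured during treatment and the text does not say whether results are withheld, but nothing shows that those judging causality see them. The table with the attribution filter is headed as guidance for routine reporting, the CRF rules in sections 10.1.1 to 10.1.4 contain no such filter, and an unfiltered Phase 1 table stands beside it. A possible rating also needs only a reasonable temporal sequence, which a calcium rise on study capsules would often meet.

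Finally, whether unactioned grade 1 values deserve to be called toxicity is partly a matter of judgment, and this is an unpowered secondary objective. That limits the weight of the point. It does not explain leaving the most direct measure of the expected harm out of the analysis.

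**Conclusion.** The concern holds in conditional form. Section 11 does not define the toxicity proportion and plans no comparison of the scheduled calcium and creatinine values. If the proportion is built from CRF adverse events, unactioned grade 1 rises are missed on both treatments. Under blinding the main result is fewer events and an absolute difference pulled toward zero, not a false excess in one arm. The size cannot be derived from the documents; the illustrated range of 8 points down to 0 rests on assumed rates, an equal recorded share on both treatments, and periods treated as independent. Equal f is a simplification: blinding equalizes the handling of the same value, but larger rises on vitamin D3 would be actioned more often. The primary PSA analysis is not affected.

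**What to change.** In section 11:

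- Name the data source, events, grades and window for the toxicity proportions, and define the comparison as all-causality.
- Add a laboratory toxicity endpoint from the scheduled values: the worst CTCAE grade per man per treatment period of albumin-corrected calcium (the protocol's own formula) and of creatinine, irrespective of management, attribution or adverse-event entry.
- Take account of the value at the start of each period, since entry allows corrected calcium up to 10.5 mg/dL. The schedule does not spell out whether the pre-study panel is repeated after washout, so state which value serves as the start of period 2.
- Analyze with within-man pairing, as the cross-over requires.

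In section 10.3, state that the attribution table governs reporting only, and say which of the two printed tables applies.

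The cost is SAP wording, one derived dataset and slightly more analysis. If an already scheduled value serves as the start of period 2, no new tests are needed. No clinical rule changes.
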